8.2.3.3. Systemic Events

During the reactogenicity e-diary reporting period, participants will be asked to assess vomiting, diarrhea, headache, fatigue, chills, new or worsened muscle pain, and new or worsened joint pain and to record the symptoms in the reactogenicity e-diary. The symptoms will be assessed by the participant as absent, mild, moderate, or severe according to the grading scale in Table 2.

If a Grade 3 systemic event is reported in the reactogenicity e-diary, a telephone contact should occur to ascertain further details and determine whether a site visit is clinically indicated. Only an investigator or medically qualified person is able to classify a participant's systemic event as Grade 4. If a participant experiences a confirmed Grade 4 systemic event, the investigator must immediately notify the sponsor and, if it is determined to be related to the administration of the study intervention, further vaccinations will be discontinued in that participant.

Table 2. Systemic Event Grading Scale

	Mild (Grade 1)	Moderate (Grade 2)	Severe (Grade 3)	Potentially Life- Threatening (Grade 4)	
Vomiting	1-2 times in 24 hours	>2 times in 24 hours	Requires IV hydration	Emergency room visit or hospitalization for hypotensive shock	
Diarrhea	2 to 3 loose stools in 24 hours	4 to 5 loose stools in 24 hours	6 or more loose stools in 24 hours	Emergency room visit or hospitalization for severe diarrhea	
Headache	Does not interfere with activity	Some interference with activity	Prevents daily routine activity	Emergency room visit or hospitalization for severe headache	
Fatigue/tiredness	Does not interfere with activity	Some interference with activity	Prevents daily routine activity	Emergency room visit or hospitalization for severe fatigue	
Chills	Does not interfere with activity	Some interference with activity	Prevents daily routine activity	Emergency room visit or hospitalization for severe chills	
New or worsened muscle pain	Does not interfere with activity	Some interference with activity	Prevents daily routine activity	Emergency room visit or hospitalization for severe new or worsened muscle pain	

PFIZER CONFIDENTIAL

Table 2. Systemic Event Grading Scale

	Mild (Grade 1)	Moderate (Grade 2)	Severe (Grade 3)	Potentially Life- Threatening (Grade 4)
New or worsened joint pain	Does not interfere with activity	Some interference with activity	Prevents daily routine activity	Emergency room visit or hospitalization for severe new or worsened joint pain

Abbreviation: IV = intravenous.

8.2.3.4. Fever

In order to record information on fever, a thermometer will be given to participants with instructions on how to measure oral temperature at home. Temperature will be collected in the reactogenicity e-diary in the evening daily during the reactogenicity e-diary reporting period. It will also be collected at any time during the reactogenicity e-diary data collection periods when fever is suspected. Fever is defined as an oral temperature ≥38.0°C (100.4°F). The highest temperature for each day will be recorded in the reactogenicity e-diary. Temperature will be measured and recorded to 1 decimal place. Temperatures recorded in degrees Fahrenheit will be programmatically converted to degrees Celsius and then categorized according to the scale shown in Table 3 during analysis.

If a fever of \geq 39.0°C (\geq 102.1°F) is reported in the reactogenicity e-diary, a telephone contact should occur to ascertain further details and determine whether a site visit is clinically indicated. Only an investigator or medically qualified person is able to confirm a participant's fever as >40.0°C (>104.0°F). If a participant experiences a confirmed fever >40.0°C (>104.0°F), the investigator must immediately notify the sponsor and, if it is determined to be related to the administration of the study intervention, further vaccinations will be discontinued in that participant.

Table 3. Scale for Fever

≥38.0-38.4°C (100.4-101.1°F)	
>38.4-38.9°C (101.2-102.0°F)	
>38.9-40.0°C (102.1-104.0°F)	
>40.0°C (>104.0°F)	

8.2.3.5. Antipyretic Medication

The use of antipyretic medication to treat symptoms associated with study intervention administration will be recorded in the reactogenicity e-diary daily during the reporting period (Day 1 through Day 7).

8.2.4. Clinical Safety Laboratory Assessments

Clinical safety laboratory assessments will be collected in both Substudies A and B. See Section 10.2.

All protocol-required laboratory assessments, as defined in Appendix 2, must be conducted in accordance with the laboratory manual and the SoA. Unscheduled clinical laboratory measurements may be obtained at any time during the study to assess any perceived safety issues.

The investigator must review the laboratory report, document this review, and record any clinically relevant changes occurring during the study in the AE section of the CRF. Refer to the laboratory normal ranges (provided separately) for grading scales for abnormalities.

Clinically significant abnormal laboratory findings are those that are not associated with the underlying disease, unless judged by the investigator to be more severe than expected for the participant's condition.

All laboratory tests with values considered clinically significantly abnormal during participation in the study or within 28 days after the last dose of study intervention should be repeated until the values return to normal or baseline or are no longer considered clinically significant by the investigator or medical monitor.

If such values do not return to normal/baseline within a period of time judged reasonable by the investigator, the etiology should be identified and the sponsor notified.

See Section 10.6 for suggested actions and follow-up assessments in the event of potential DILI.

8.2.5. Pregnancy Testing

Following screening, pregnancy tests may be urine or serum tests, but must have a sensitivity of at least 25 mIU/mL. Pregnancy tests will be performed in WOCBP at the times listed in the SoA, immediately before the administration of each vaccine dose. A negative pregnancy test result will be required prior to the participant's receiving the study intervention. Pregnancy tests may also be repeated if requested by IRBs/ECs or if required by local regulations. In the case of a positive confirmed pregnancy, the participant will not be administered the study intervention dose and will be withdrawn from the study.

8.2.6. Stopping Rules

The following stopping rules are in place for both Substudies A and B; see also Section 10.9.8.6 and Section 10.10.8.6, respectively.

8.2.7. ECGs and Echocardiograms

ECGs will be collected at the times specified in Section 10.9.1 for Substudy A and Section 10.10.1 for Substudy B.

All scheduled 12-lead ECGs should be performed after the participant has rested quietly for at least 10 minutes in a supine position. The ECGs should be obtained prior to blood collection, measurement of blood pressure, and measurement of pulse rate. ECGs will be performed in triplicate.

ECG data will be submitted to a central laboratory for measurement. The final ECG report from the central laboratory should be maintained in the participant's source documentation and be the final interpretation of the ECG recording. Any clinically significant changes from the baseline/Day 1 ECG may potentially be AEs (Appendix 5) and should be evaluated further, as clinically warranted.

In some cases, it may be appropriate to repeat abnormal ECGs to rule out improper lead placement as contributing to the ECG abnormality. It is important that lead placement be in the same position each time in order to achieve precise ECG recordings.

ECG values of potential clinical concern are listed in Appendix 5.

ECG abnormalities consistent with probable or possible myocarditis or pericarditis are those judged as such by a cardiologist, including:

- Sustained atrial or ventricular arrhythmias
- Second-degree Mobitz Type II or worse AV block, new bundle branch block
- Diffuse ST-segment elevation or PR-segment inversion, compatible with pericarditis

Echocardiograms may be performed as detailed in Section 10.9.8.8.11 and Section 10.10.8.8.11.

8.3. Adverse Events, Serious Adverse Events, and Other Safety Reporting

The definitions of an AE and an SAE can be found in Appendix 3.

The definitions of device-related safety events (ADEs and SADEs) can be found in Section 10.7. Device deficiencies are covered in Section 8.3.9.

AEs may arise from symptoms or other complaints reported to the investigator by the participant (or, when appropriate, by a caregiver, surrogate, or the participant's legally authorized representative), or they may arise from clinical findings of the investigator or other healthcare providers (clinical signs, test results, etc.).

The investigator and any qualified designees are responsible for detecting, documenting, and recording events that meet the definition of an AE or SAE and remain responsible to pursue and obtain adequate information both to determine the outcome and to assess whether the event meets the criteria for classification as an SAE or caused the participant to discontinue the study intervention (see Section 7.1).

During the active collection period as described in Section 8.3.1, each participant will be questioned about the occurrence of AEs in a nonleading manner.

In addition, the investigator may be requested by Pfizer Safety to obtain specific follow-up information in an expedited fashion.

8.3.1. Time Period and Frequency for Collecting AE and SAE Information

The time period for actively eliciting and collecting AEs and SAEs ("active collection period") for each participant begins from the time the participant provides informed consent, which is obtained before the participant's participation in the study (ie, before undergoing any study-related procedure and/or receiving study intervention), through and including:

- Visit 4 (4-week follow-up visit), and from Visit 5 to Visit 5B (4-week post-Vaccination 2 follow-up visit) for Substudy A. Additionally, for Substudy A, any AEs occurring up to 48 hours after the blood draws at Visits 4 and 5B must be recorded on the CRF.
- Visit 206 (4-week follow-up visit) for Substudy B. Additionally, for Substudy B, any AEs occurring up to 48 hours after the blood draws at Visits 206 and 207 must be recorded on the CRF.

SAEs will be collected from the time the participant provides informed consent to approximately 6 months after the participant's last study vaccination (Visit 6 for Substudy A and Visit 208 for Substudy B).

Follow-up by the investigator continues throughout and after the active collection period and until the AE or SAE or its sequelae resolve or stabilize at a level acceptable to the investigator.

For participants who are screen failures, the active collection period ends when screen failure status is determined.

If the participant withdraws from the study and also withdraws consent for the collection of future information, the active collection period ends when consent is withdrawn.

If a participant permanently discontinues or temporarily discontinues study intervention because of an AE or SAE, the AE or SAE must be recorded on the CRF and the SAE reported using the Vaccine SAE Reporting Form.

Investigators are not obligated to actively seek information on AEs or SAEs after the participant has concluded study participation. However, if the investigator learns of any SAE, including a death, at any time after a participant has completed the study, and he/she considers the event to be reasonably related to the study intervention, the investigator must promptly report the SAE to Pfizer using the Vaccine SAE Reporting Form.

8.3.1.1. Reporting SAEs to Pfizer Safety

All SAEs occurring in a participant during the active collection period as described in Section 8.3.1 are reported to Pfizer Safety on the Vaccine SAE Reporting Form immediately upon awareness and under no circumstance should this exceed 24 hours, as indicated in Appendix 3. The investigator will submit any updated SAE data to the sponsor within 24 hours of it being available.

8.3.1.2. Recording Nonserious AEs and SAEs on the CRF

All nonserious AEs and SAEs occurring in a participant during the active collection period, which begins after obtaining informed consent as described in Section 8.3.1, will be recorded on the AE section of the CRF.

The investigator is to record on the CRF all directly observed and all spontaneously reported AEs and SAEs reported by the participant.

8.3.2. Method of Detecting AEs and SAEs

The method of recording, evaluating, and assessing causality of AEs and SAEs and the procedures for completing and transmitting SAE reports are provided in Appendix 3.

Care will be taken not to introduce bias when detecting AEs and/or SAEs. Open-ended and nonleading verbal questioning of the participant is the preferred method to inquire about AE occurrences.

8.3.3. Follow-Up of AEs and SAEs

After the initial AE or SAE report, the investigator is required to proactively follow each participant at subsequent visits/contacts. For each event, the investigator must pursue and obtain adequate information until resolution, stabilization, the event is otherwise explained, or the participant is lost to follow-up (as defined in Section 7.3).

In general, follow-up information will include a description of the event in sufficient detail to allow for a complete medical assessment of the case and independent determination of possible causality. Any information relevant to the event, such as concomitant medications and illnesses, must be provided. In the case of a participant death, a summary of available autopsy findings must be submitted as soon as possible to Pfizer Safety.

Further information on follow-up procedures is given in Appendix 3.

8.3.4. Regulatory Reporting Requirements for SAEs

Prompt notification by the investigator to the sponsor of an SAE is essential so that legal obligations and ethical responsibilities toward the safety of participants and the safety of a study intervention under clinical investigation are met.

The sponsor has a legal responsibility to notify both the local regulatory authority and other regulatory agencies about the safety of a study intervention under clinical investigation.

The sponsor will comply with country-specific regulatory requirements relating to safety reporting to the regulatory authority, IRBs/ECs, and investigators.

Investigator safety reports must be prepared for SUSARs according to local regulatory requirements and sponsor policy and forwarded to investigators as necessary.

An investigator who receives SUSARs or other specific safety information (eg, summary or listing of SAEs) from the sponsor will review and then file it along with the SRSD(s) for the study and will notify the IRB/EC, if appropriate according to local requirements.

8.3.5. Environmental Exposure, Exposure During Pregnancy or Breastfeeding, and Occupational Exposure

Environmental exposure occurs when a person not enrolled in the study as a participant receives unplanned direct contact with or exposure to the study intervention. Such exposure may or may not lead to the occurrence of an AE or SAE. Persons at risk for environmental exposure include healthcare providers, family members, and others who may be exposed. An environmental exposure may include exposure during pregnancy, exposure during breastfeeding, and occupational exposure.

Any such exposure to the study intervention under study are reportable to Pfizer Safety within 24 hours of investigator awareness.

8.3.5.1. Exposure During Pregnancy

An EDP occurs if:

- A female participant is found to be pregnant while receiving or after discontinuing study intervention.
- A male participant who is receiving or has discontinued study intervention exposes a female partner prior to or around the time of conception.
- A female is found to be pregnant while being exposed or having been exposed to study intervention due to environmental exposure. Below are examples of environmental EDP:
 - A female family member or healthcare provider reports that she is pregnant after having been exposed to the study intervention by inhalation or skin contact.
 - A male family member or healthcare provider who has been exposed to the study intervention by inhalation or skin contact then exposes his female partner prior to or around the time of conception.

The investigator must report EDP to Pfizer Safety within 24 hours of the investigator's awareness, irrespective of whether an SAE has occurred. The initial information submitted should include the anticipated date of delivery (see below for information related to termination of pregnancy).

- If EDP occurs in a participant or a participant's partner, the investigator must report this information to Pfizer Safety on the Vaccine SAE Reporting Form and an EDP Supplemental Form, regardless of whether an SAE has occurred. Details of the pregnancy will be collected after the start of study intervention and until 28 days after the last dose of study intervention.
- If EDP occurs in the setting of environmental exposure, the investigator must report information to Pfizer Safety using the Vaccine SAE Reporting Form and EDP Supplemental Form. Since the exposure information does not pertain to the participant enrolled in the study, the information is not recorded on a CRF; however, a copy of the completed Vaccine SAE Reporting Form is maintained in the investigator site file.

Follow-up is conducted to obtain general information on the pregnancy and its outcome for all EDP reports with an unknown outcome. The investigator will follow the pregnancy until completion (or until pregnancy termination) and notify Pfizer Safety of the outcome as a follow-up to the initial EDP Supplemental Form. In the case of a live birth, the structural integrity of the neonate can be assessed at the time of birth. In the event of a termination, the reason(s) for termination should be specified and, if clinically possible, the structural integrity of the terminated fetus should be assessed by gross visual inspection (unless preprocedure test findings are conclusive for a congenital anomaly and the findings are reported).

Abnormal pregnancy outcomes are considered SAEs. If the outcome of the pregnancy meets the criteria for an SAE (ie, ectopic pregnancy, spontaneous abortion, intrauterine fetal demise, neonatal death, or congenital anomaly), the investigator should follow the procedures for reporting SAEs. Additional information about pregnancy outcomes that are reported to Pfizer Safety as SAEs follows:

- Spontaneous abortion including miscarriage and missed abortion;
- Neonatal deaths that occur within 1 month of birth should be reported, without regard to
 causality, as SAEs. In addition, infant deaths after 1 month should be reported as SAEs
 when the investigator assesses the infant death as related or possibly related to exposure
 to the study intervention.

Additional information regarding the EDP may be requested by the sponsor. Further follow-up of birth outcomes will be handled on a case-by-case basis (eg, follow-up on preterm infants to identify developmental delays). In the case of paternal exposure, the investigator will provide the participant with the Pregnant Partner Release of Information Form to deliver to his partner. The investigator must document in the source documents that the participant was given the Pregnant Partner Release of Information Form to provide to his partner.

8.3.5.2. Exposure During Breastfeeding

An exposure during breastfeeding occurs if:

- A female participant is found to be breastfeeding while receiving or after discontinuing study intervention.
- A female is found to be breastfeeding while being exposed or having been exposed to study intervention (ie, environmental exposure). An example of environmental exposure during breastfeeding is a female family member or healthcare provider who reports that she is breastfeeding after having been exposed to the study intervention by inhalation or skin contact.

The investigator must report exposure during breastfeeding to Pfizer Safety within 24 hours of the investigator's awareness, irrespective of whether an SAE has occurred. The information must be reported using the Vaccine SAE Reporting Form. When exposure during breastfeeding occurs in the setting of environmental exposure, the exposure information does not pertain to the participant enrolled in the study, so the information is not recorded on a CRF. However, a copy of the completed Vaccine SAE Reporting Form is maintained in the investigator site file.

An exposure during breastfeeding report is not created when a Pfizer drug specifically approved for use in breastfeeding women (eg, vitamins) is administered in accord with authorized use. However, if the infant experiences an SAE associated with such a drug, the SAE is reported together with the exposure during breastfeeding.

8.3.5.3. Occupational Exposure

The investigator must report any instance of occupational exposure to Pfizer Safety within 24 hours of the investigator's awareness using the Vaccine SAE Reporting Form, regardless of whether there is an associated SAE. Since the information about the occupational exposure does not pertain to a participant enrolled in the study, the information is not recorded on a CRF; however, a copy of the completed Vaccine SAE Reporting Form must be maintained in the investigator site file.

8.3.6. Cardiovascular and Death Events

Not applicable.

8.3.7. Disease-Related Events and/or Disease-Related Outcomes Not Qualifying as AEs or SAEs

Not applicable.

8.3.8. Adverse Events of Special Interest

For all study phases, the following events are considered AESIs:

• A confirmed diagnosis of influenza;

• A confirmed diagnosis of myocarditis or pericarditis. See Section 10.9.8.8.11 and Section 10.10.8.8.11 for additional procedures for monitoring of potential myocarditis or pericarditis in Substudies A and B, respectively.

AESIs are examined as part of routine safety data review procedures throughout the clinical trial and as part of signal detection processes.

All AESIs must be reported as an AE or SAE following the procedures described in Sections 8.3.1 through Section 8.3.4. An AESI is to be recorded as an AE or SAE on the CRF. In addition, an AESI that is also an SAE must be reported using the Vaccine SAE Reporting Form.

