6.8. Concomitant Therapy

The following concomitant medications and vaccinations will be recorded in the CRF:

- Prior receipt of any COVID-19 vaccine.
- For Substudy A, licensed influenza vaccine, if received during the prior influenza season.
- For Substudy B, any licensed influenza vaccine received in the prior 12 months.
- Any vaccinations received from 28 days prior to study enrollment until the last visit (Visit 6 for Substudy A and Visit 207 for Substudy B).
- Prohibited medications listed in Section 6.8.1 will be recorded and include start and stop dates, name of the medication, dose, unit, route, and frequency.
- All current medications at baseline will be recorded and include start date, name of the medication, dose, unit, route, and frequency.

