6.8.1. Prohibited During the Study

Receipt of the following vaccines and medications during the time periods listed below may exclude a participant from the per-protocol analysis from that point onward and may require vaccinations to be discontinued in that participant; however, it is anticipated that the participant would not be withdrawn from the study (see Section 7). Medications should not be withheld if required for a participant's medical care.

- Unless considered medically necessary, no vaccines other than study intervention should be administered within 28 days before and 28 days after each study vaccination.
- Receipt of any mRNA-platform SARS-CoV-2 vaccine within 60 days before and 60 days after study vaccination that contains modRNA for Substudy A, and within 28 days before and 28 days after any study vaccination that contains modRNA for Substudy B.
- For Substudy A, receipt of any other (nonstudy) seasonal influenza vaccine at any time during study participation is prohibited.
- For Substudy B, receipt of any other (nonstudy) seasonal influenza vaccine from enrollment to Visit 207 (8-week follow-up visit) is prohibited.
- Receipt of chronic systemic treatment with known immunosuppressant medications, or radiotherapy, within 60 days before enrollment through conclusion of the study is prohibited.
- Receipt of systemic corticosteroids (≥20 mg/day of prednisone or equivalent) for ≥14 days is prohibited from 28 days prior to enrollment through 28 days after administration of the last study intervention.
- Receipt of blood/plasma products or immunoglobulins within 60 days before enrollment through conclusion of the study is prohibited.
- Prophylactic antipyretics and other pain medication to prevent symptoms associated with study intervention administration are not permitted. However, if a participant is taking a medication for another condition, even if it may have antipyretic or pain-relieving properties, it should not be withheld prior to study vaccination.

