10.3.1. Definition of AE

AE Definition

- An AE is any untoward medical occurrence in a patient or clinical study participant, temporally associated with the use of study intervention, whether or not considered related to the study intervention.
- Note: An AE can therefore be any unfavorable and unintended sign (including an abnormal laboratory finding), symptom, or disease (new or exacerbated) temporally associated with the use of study intervention.

Events Meeting the AE Definition

- Any abnormal laboratory test results (hematology, clinical chemistry, or urinalysis) or other safety assessments (eg, ECG, radiological scans, vital sign measurements), including those that worsen from baseline, considered clinically significant in the medical and scientific judgment of the investigator. Any abnormal laboratory test results that meet any of the conditions below must be recorded as an AE:
 - Is associated with accompanying symptoms.
 - Requires additional diagnostic testing or medical/surgical intervention.
 - Leads to a change in study dosing (outside of any protocol-specified dose adjustments) or discontinuation from the study, significant additional concomitant drug treatment, or other therapy.
- Exacerbation of a chronic or intermittent preexisting condition, including either an increase in frequency and/or intensity of the condition.
- New condition detected or diagnosed after study intervention administration, even though it may have been present before the start of the study.
- Signs, symptoms, or the clinical sequelae of a suspected drug-drug interaction.
- Signs, symptoms, or the clinical sequelae of a suspected overdose of either study intervention or a concomitant medication. Overdose per se will not be reported as an AE or SAE unless it is an intentional overdose taken with possible suicidal/self-harming intent. Such overdoses should be reported regardless of sequelae.

Events NOT Meeting the AE Definition

- Any clinically significant abnormal laboratory findings or other abnormal safety assessments that are associated with the underlying disease, unless judged by the investigator to be more severe than expected for the participant's condition.
- The disease/disorder being studied or expected progression, signs, or symptoms of the disease/disorder being studied, unless more severe than expected for the participant's condition.
- Medical or surgical procedure (eg, endoscopy, appendectomy): the condition that leads to the procedure is the AE.

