- Complete the source documents.
- The investigator or an authorized designee completes the CRFs.

10.10.8.8.9. Visit 208 – 6-Month Follow-up Telephone Contact – 175 to 189 Days After Last Study Vaccination

Visit 208 is to be conducted within 175 to 189 days after Visit 201 or 203, depending on if the participant is assigned to a 1- or 2-visit vaccination schedule.

- Contact the participant by telephone.
- Record AEs as described in Section 8.3.
- Record nonstudy vaccinations as described in Section 6.8.
- Complete the source documents.
- The investigator or an authorized designee completes the CRFs.

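### In Substudy B, nonserious AESIs, including confirmed influenza, need not be collected for most of the interval before the 8-week HAI sample or for most of the follow-up after it

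*Protocol*

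**What the plan says.** Protocol 8.3.8 lists two AESIs for every study phase. One is "A confirmed diagnosis of influenza"; the other is confirmed myocarditis or pericarditis. It adds that "AESIs are examined as part of routine safety data review procedures throughout the clinical trial". The section sets no collection period of its own: "All AESIs must be reported as an AE or SAE following the procedures described in Sections 8.3.1 through Section 8.3.4".

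Protocol 8.3.1 ends active AE collection for Substudy B at Visit 206, the 4-week follow-up visit, with one extension: "any AEs occurring up to 48 hours after the blood draws at Visits 206 and 207 must be recorded on the CRF". SAEs are collected to Visit 208, about 6 months after the last vaccination. Section 8.3.1.2 ties CRF recording of nonserious AEs to the active period and also asks for spontaneously reported AEs to be recorded. SAP 3.1.1.5 repeats these windows.

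The 8-week HAI results (GMT, GMFR, seroconversion, titer at or above 1:40) are secondary endpoints in Protocol 10.10.3. For them, SAP 2.2.2 names three intercurrent events: discontinuation, major protocol violation and out-of-window blood draws. Influenza infection is not among them. SAP 3.1.1.5 lists the AESIs, but the AE and SAE summaries in SAP 6.1.1.3 and 6.1.1.4 have no AESI category.

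For nonstudy vaccines, Protocol 6.8 requires recording "until the last visit (Visit 6 for Substudy A and Visit 207 for Substudy B". The Substudy B schedule of activities marks this item at every contact through Visit 208. The Visit 208 procedures carry the same line as the other visits: "Record nonstudy vaccinations as described in Section 6.8".

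**The concern.** The plan singles out two diagnoses for review over the whole trial, then collects their nonserious forms for about the first month after the last dose. Influenza is also an immunological event. A case between Visits 206 and 207 can raise the HAI titer measured at Visit 207, and the database need not contain anything that shows it.

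Two things are at stake. First, 8-week GMTs, fold rises and seroconversion rates could mix vaccine response with response to infection, and the analyst could not tell which participants were affected. The protocol's summary of changes expects that enrollment may run into the 2022 northern hemisphere influenza season, so the possibility is foreseeable. Second, a count of confirmed influenza or of nonserious myocarditis or pericarditis would be complete only for the early window, although 8.3.8 promises review throughout.

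**Working it through.** There is no figure in the plan to reproduce: the study is descriptive and the point concerns collection windows. The check is interval arithmetic on the visit windows.

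**Inputs** (Protocol 10.10.1 and 10.10.8.8.7 to 10.10.8.8.9, days after the last vaccination): Visit 206, 26-30; Visit 207, 52-60; Visit 208, 175-189. Post-draw allowance: 48 hours, or 2 days, after each of the Visit 206 and 207 draws (8.3.1).

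**Formula.** Shortest gap = earliest later visit − latest earlier visit. Longest gap = latest later visit − earliest earlier visit.

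| Interval | Shortest | Longest | Net of post-draw allowance |
|---|---|---|---|
| Visit 206 to 207 | 52 − 30 = 22 | 60 − 26 = 34 | less 2: 20-32 days |
| Visit 207 to 208 | 175 − 60 = 115 | 189 − 52 = 137 | less 2: 113-135 days |
| Visit 206 to 208 | 175 − 30 = 145 | 189 − 26 = 163 | less 4: 141-159 days |

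As a share of follow-up after the last dose: 141/175 = 81% to 159/189 = 84%.

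The 48 hours after the Visit 207 draw cannot help the 8-week titer, because they follow the sample. The AE lines in the Visit 207 and 208 procedures do not extend the window either, since they refer back to Section 8.3. No blood is drawn at Visit 208, so the titer question is confined to the 20-32 days before Visit 207. The later period matters only for the completeness of AESI data.

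**Illustrative effect on the 8-week GMT.** The documents give no attack rate and no titer rise after infection, so both are assumptions. If a fraction p of a group is infected in the interval and each infection multiplies the titer by 4, the GMT is multiplied by 4^p:

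- p = 1%: 4^0.01 = 1.014, or +1.4%
- p = 5%: 4^0.05 = 1.072, or +7.2%
- p = 10%: 4^0.10 = 1.149, or +14.9%

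The seroconversion proportion could rise by at most p. SAP 5.2 analyzes initial and expanded enrollment separately, so group size matters. Under the same 4-fold assumption, one case in a group of 15 gives 4^(1/15) = 1.097 (+9.7%), and one case in 120 gives 4^(1/120) = 1.012 (+1.2%). With 120 participants and an assumed 1% risk, 1.2 cases are expected and the chance of at least one is 1 − 0.99^120 = 0.70, which matches the N = 120 row of Protocol Table 4.

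**The case against.** The best defense is that the windows match the declared primary estimands: AEs to 4 weeks and SAEs to 6 months. On that view a longer AESI window is a preference, not the repair of an error. This stands in part. Nothing in the primary safety analysis is wrong, but 8.3.8 sets a wider aim for AESIs than the window serves, and the primary AE window was not chosen to protect the 8-week titer.

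Two further objections stand. The effect sizes rest on assumed rates, and at 1% infected the GMT moves by only 1.4% in a study without hypothesis tests. Also, Protocol 2.2.1 notes that influenza may often be asymptomatic and the Substudy B schedule contains no influenza test, so collecting diagnoses leaves other infections unseen.

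Four stronger readings are tempting, and the documents do not support them:

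- **That later AESIs go unrecorded.** Serious ones are collected to Visit 208, spontaneous reports are to be recorded (8.3.1.2), and participants are asked at Visits 206 and 207 to contact the site about medically attended events. The accurate statement is that collection of nonserious cases is not required.
- **That nonstudy vaccines stop being recorded at Visit 207.** The schedule and the Visit 208 procedures call for them at 6 months. Section 6.8 conflicts with those places; it does not override them.
- **That a late myocarditis SAE could not be separated from an intervening mRNA COVID-19 vaccine.** Section 8.3.3 requires relevant information such as concomitant medications to be supplied for any event, and Appendix 3 requires alternative causes and timing to be weighed.
- **That sites would leave influenza out under Appendix 3.** Its list of events that are not AEs includes "The disease/disorder being studied or expected progression, signs, or symptoms of the disease/disorder being studied, unless more severe than expected", but that is general text. Section 8.3.8 specifically requires AESIs to be recorded as an AE or SAE, and 8.3.7 declares disease-related events outside AE reporting not applicable.

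**Conclusion.** The point holds for the AESI window. Required collection of nonserious AESIs in Substudy B ends at Visit 206 plus the two 48-hour post-draw periods. That leaves out about 20-32 of the 22-34 days before the 8-week HAI sample and about 141-159 days in all up to Visit 208. These figures follow from the protocol's visit windows alone. The SAP offers no way to find 8-week titers that follow an infection.

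The effect on the titers is not known from the documents. It depends on how many participants are infected in the interval and by how much their titers rise. It would be small in groups of 120 unless infection were common, and more visible in groups of 15. It does not touch the 1-week or 4-week results, and it does not invalidate the descriptive analysis. It limits what can be said about the 8-week results and about AESI frequency.

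The nonstudy-vaccine point is a secondary inconsistency. Section 6.8 names Visit 207 as the last visit, while the schedule and the Visit 208 procedures continue to the 6-month contact. It deserves correction because 6.8.1 states that "receipt of any other (nonstudy) seasonal influenza vaccine from enrollment to Visit 207 (8-week follow-up visit) is prohibited", so that prohibition lapses at the very visit where 6.8 says recording ends, while SAEs are still collected.

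**What to change.** 1. **Protocol 8.3.1 and SAP 3.1.1.5:** state that the AESIs in 8.3.8, serious or not, are collected through Visit 208 in Substudy B, by a question at the existing Visit 207 and 208 contacts.
2. **SAP 6.1.1.3:** add an AESI tabulation by vaccine group, with its own window to Visit 208.
3. **SAP 6.2:** flag 8-week HAI results that follow a recorded influenza case, or show a sensitivity summary without them.
4. **Protocol 6.8:** reconcile the Visit 207 end point for nonstudy-vaccine recording with the schedule of activities and the Visit 208 procedures.
5. **Appendix 3 (optional):** add a sentence that the 8.3.8 AESIs are recorded despite the exception for the disease being studied.

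The cost is wording changes, one question at two contacts that already take place, a table and a flag. The downside is a few extra CRF entries. Capture stays limited to diagnosed cases, so the flagged summary would reduce the ambiguity in the 8-week titers, not remove it.
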